## 1. INTRODUCTION

### 1.1. Study Summary

Inherited cardiac conditions (ICC) comprise any hereditary condition, which may affect heart muscle, vasculature, or heart electrical conductive system. ICCs represent a major cause of heart disease in all age groups, and have significant implications for patients and their families. Symptoms vary considerably, from no symptoms to sudden death. Our understanding of these conditions has increased over the past decade, however significant limitations remains in diagnosis and risk stratification of these patients and their families.

The NIH has defined a biomarker as “a characteristic that is objectively measured and evaluated as an indicator of normal biological processes, pathogenic processes, or pharmacologic responses to a therapeutic intervention”.

This study aims to investigate the utility of biomarkers in a large cohort of patients with inherited cardiac conditions with the aim of improving diagnosis and risk stratification. Biomarkers will be related to the presence and severity of cardiovascular disease and other markers of cardiac disease.

As part of this study, all patients with or with suspected ICCs attending clinics in Manchester (University Hospital of South Manchester (UHSM) and Central Manchester University Hospitals (CMFT)) will be approached over a 5 year period. The expectation is to recruit 1000 patients. Patients will undergo their clinic appointments in the usual manner. As part of the study, clinical parameters collected as part of routine care (e.g. clinical history, imaging findings, blood test results, genetic information) will be assessed in relation to each other and in relation to patient outcome over subsequent 10 year follow-up. In addition, a peripheral blood sample of up to approximately 20mL will be taken and stored to allow measurement of blood biomarkers relating to the heart, including genetic analysis, which will be related to the clinical parameters and outcome.

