#### **4.2. Inclusion Criteria**

Any adult patient attending a hospital clinic that specialises in the management of patients with ICCs at UHSM or CMFT.

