#### **4.3. Exclusion Criteria**

Age < 16 years, imprisonment, inability to provide informed consent.

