##### **4.6.1. Clinic Visit**

Patients will attend clinic, and any additional clinically indicated hospital appointments, in the usual manner. A peripheral blood sample of up to approximately 20mL will be taken for blood markers of cardiac disease and genetic analysis. Clinical data, including that relating to any imaging, blood test or functional investigations, will be recorded.

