##### **4.6.2. Cardiovascular status**

Follow-up information regarding cardiovascular disease status, demographics and concurrent medical conditions and treatments will be obtained over the 10 year period following the clinic visit using the following methods:

1. GP and hospital medical records.
2. Central UK bodies, registries, audits and databases (e.g. HSCIC, ONS, NICOR, MINAP) and local health bodies e.g. clinical commissioning groups.
3. Phone call to patients

None of these follow-up procedures will occur more than once yearly.

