### **5. STATISTICAL PLAN**

#### **5.1. Sample Size and Power Calculation**

We will ask each adult patient scheduled to attend hospital clinics that specialise in the management of patients with ICCs at UHSM and CMFT to participate in this research study. The expectation is that over a 5 year period, approximately 200 participants per year may be enrolled in this study. Due to the diversity of the variables being collected, all patients who sign consent will provide meaningful information for this study.

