#### **5.2. Statistical Analysis**

Multivariable regression modelling will be used to examine relationships between cardiac biomarkers and cardiovascular disease while adjusting for baseline differences of subjects. Chi square or Fisher exact tests will be used to compare categorical variables between patients with different marker levels. Independent samples t tests or Mann Whitney U tests will be used to compare continuous variables between patients with differing marker levels. Survival analysis will use logrank testing and Cox regression.

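### Relatives can enrol in this hereditary-disease cohort, but section 5.2 states no allowance for family clustering and no section mentions recording family membership

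*Combined protocol and SAP*

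**What the plan says.** **Who can enrol.** Section 4.2 admits "Any adult patient attending a hospital clinic that specialises in the management of patients with ICCs at UHSM or CMFT". Section 5.1 makes the approach universal: "We will ask each adult patient scheduled to attend hospital clinics". The exclusions in section 4.3 are only "Age < 16 years, imprisonment, inability to provide informed consent". Nothing limits enrolment to one member of a family.

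**What is measured.** Under section 4.6.1 a blood sample "will be taken for blood markers of cardiac disease and genetic analysis". Section 1.1 defines the conditions as hereditary and says that "significant limitations remains in diagnosis and risk stratification of these patients and their families".

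**How it is analysed.** Section 5.2 is the whole analysis plan. For continuous variables, "Independent samples t tests or Mann Whitney U tests will be used to compare continuous variables between patients with differing marker levels". Chi-square or Fisher tests cover categorical variables. Logrank tests and Cox regression cover survival, and multivariable regression adjusts for baseline differences. No variance estimator, random effect or frailty term is named.

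**What is recorded about families.** Section 6.1 describes one identifier per participant. No section mentions family membership as a data item, although the CRF fields are not listed.

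**The concern.** The three kinds of unadjusted comparison (chi-square or Fisher, t or Mann-Whitney, logrank) treat patients as independent in their standard form. Relatives may resemble each other on a genetic marker and on the outcome. If both hold, each extra relative adds less information than an unrelated patient, and the usual standard error is too small. If relatives differ on the marker, for example a carrier and a non-carrier from one family, the usual standard error is too large. If the marker is uncorrelated within families, it is correct.

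Adjusting for baseline differences changes the model for the mean. It does not by itself deal with correlated errors, although the correlation that remains after adjustment may be smaller.

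What is at stake is the stated precision for familial markers: intervals may be too narrow and associations may look more certain than they are. Without a family code, neither the study team nor outside users of the shared data (section 8) can readily see whether this matters.

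**Working it through.** **The plan's own figure.** Section 5.1 expects about 200 participants a year for 5 years: 200 × 5 = 1000, which agrees with section 1.1. This is a recruitment expectation. No alpha, power or effect size is given, so there is no power figure to reproduce.

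**Inputs.** The documents give no family sizes, within-family correlations or alpha. All of these are assumed below, with a nominal two-sided 5% as the yardstick.

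**Formula.** Let f be the share of patients in families of size m, ρx the within-family correlation of the marker, and ρy that of the outcome on its observed scale.

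- Variance factor: DE = 1 + f(m − 1)ρxρy
- Actual error: 2[1 − Φ(1.96/√DE)]
- A median split turns a continuous correlation r into (2/π)·arcsin(r): 0.3 becomes 0.194 and 0.5 becomes 0.333.

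| Assumed case | DE | Error |
|---|---|---|
| A. 30% in pairs, ρx 0.3, ρy 0.3 | 1 + 0.3×1×0.3×0.3 = 1.027 | 5.31% |
| A with the marker split, ρx 0.194 | 1.017 | 5.20% |
| B. 10% in pairs, shared marker (ρx 1), ρy 0.3 | 1.03 | 5.35% |
| C. 30% in pairs, shared marker, ρy 0.3 | 1.09 | 6.05% |
| D. Half in threes, split marker ρx 0.333, ρy 0.5 | 1.167 | 6.96% |
| E. Half in threes, shared marker, ρy 0.5 | 1 + 0.5×2×1×0.5 = 1.5 | 10.95% |
| F. 30% in discordant pairs (ρx −1), ρy 0.5 | 0.85 | 3.35% |

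**Threshold.** Error reaches 6% at DE = (1.960/1.881)² = 1.086. With a shared marker and ρy 0.3, this needs f(m − 1) = 0.086/0.3 = 0.287, or about 29% of patients in pairs. With ρx 0.333 and ρy 0.3 it needs 0.860, or about 86% in pairs.

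**Adjusted models.** Null simulation: 30,000 runs, 1000 patients, a binary marker, two independent baseline covariates, about 30% with the binary outcome and about 20% with an event in 10 years. Correlations are residual, and latent for binary and survival outcomes. The Monte Carlo standard error is about 0.13 points at 5%. Each cell is unclustered / family-clustered robust error, in %.

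| Case | Linear | Logistic | Cox |
|---|---|---|---|
| A, split marker | 5.08 / 4.95 | 5.16 / 5.04 | 5.14 / 5.07 |
| C | 6.04 / 5.15 | 5.77 / 5.26 | 5.70 / 5.14 |
| D | 7.13 / 5.27 | 6.19 / 5.02 | 5.98 / 4.90 |
| E | 10.81 / 4.90 | 8.84 / 5.19 | 8.21 / 4.88 |
| F | 3.49 / 5.21 | 4.11 / 5.08 | 3.90 / 4.89 |

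The lower logistic and Cox figures in case E come from the outcome scale, not from adjustment. An unadjusted test of a 30% binary outcome with latent correlation 0.5 gives about 8.7% to 8.9%, not 11%.

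**Uncommon markers.** The good performance of robust errors above holds for common markers only. Null linear model without covariates, 1000 patients, family-shared marker, about 10,000 runs; unclustered / clustered, in %:

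| Marker frequency (assumed) | Case C families | Case E families |
|---|---|---|
| 1% | 5.4 / 11.7 | 10.4 / 17.6 |
| 2% | 5.7 / 8.0 | 10.3 / 9.7 |
| 5% | 6.3 / 6.2 | 11.0 / 7.0 |

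A separate simulation at 1% gave 6.0 / 12.6 and 10.0 / 17.3. With few carrier families, the plain robust variance rests on too few clusters.

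**The case against.** The strongest reply is that section 5.2 is four sentences long and silent on variance estimation, and that silence is not a commitment to independence. This stands for the regression and Cox models: a clustered variance would be compatible with the text. Likewise, the words independent samples are the name of the unpaired two-group test, not a claim that patients are unrelated. The omission remains, because no section states an allowance.

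A second reply is that the milder cases are negligible. This also stands. Cases A and B barely move the error. Only D and E exceed 6.1%, and both put half the cohort in families of three, which nothing in the documents supports.

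A third is that kinship might be recovered later from "clinical history, imaging findings, blood test results, genetic information" (section 1.1), from "GP and hospital medical records" or phone calls (section 4.6.2), or from the identifiers held under section 6.3. It might, in part, but asking at enrolment is easier.

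A fourth is that the obvious remedy, plain family-clustered robust errors throughout, can be worse than the fault. For uncommon markers this is right, and the fix below allows for it.

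The reference to families in section 1.1 is background. A reader might infer a plan to recruit relatives, but the documents show only that relatives may enrol.

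**Conclusion.** The point holds as a low-cost improvement worth considering. Eligibility permits relatives, the named unadjusted tests assume independent patients, and no allowance for clustering or recording of families is stated.

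Its size depends wholly on assumed family structure and correlations, against an assumed nominal 5%:

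- about 5.1% to 5.3% with few relatives or weakly familial markers;
- about 5.7% to 6.1% with 30% in pairs, a fully shared marker and outcome correlation 0.3;
- about 11% for continuous outcomes, and 8% to 9% for binary or survival outcomes (latent correlation), only if half the cohort is in families of three with a fully shared marker and outcome correlation 0.5;
- about 3.4% to 4.1% with 30% in discordant pairs and outcome correlation 0.5.

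Three stronger readings are tempting and unsupported. The documents do not show that error will be seriously inflated, since they do not say how many relatives will enrol. They do not show that inflation is the only direction, since patients with merely suspected disease are also approached and relatives may differ on the marker. And nothing here implies that the estimated associations are biased.

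**What to change.** - **Data.** Record a pseudonymised family code at enrolment, and report the number and size of enrolled families.
- **Models.** State in section 5.2 that the regression and Cox models allow for family clustering. Use family-clustered robust standard errors where many families carry each marker level. For uncommon markers (roughly under 5%, or few carrier families), name a small-cluster correction or a mixed or shared-frailty model. Those alternatives were not simulated here, so their error should be checked against the family structure actually enrolled.
- **Unadjusted tests.** Label them descriptive.
- **Sensitivity analysis.** Repeat the models with one member per family, chosen by a pre-stated rule, for example at random with a fixed seed. The rule matters because taking the index case and choosing at random give different populations.

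**Cost.** One data item and a few sentences, with no extra patients or visits. Some effort is needed to establish kinship across two hospitals and to keep the code compatible with storage under section 6.3 and data sharing under section 8. Intervals for familial markers widen by √DE: about 4% in case C (√1.09 = 1.044). In case E it is 22% for continuous outcomes (√1.5 = 1.22), and the simulated errors imply about 15% for logistic and 13% for Cox models. In case F they narrow by about 8% (√0.85 = 0.92).

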## 2. BACKGROUND

Inherited cardiac conditions (ICC) comprise any hereditary condition, which may affect heart muscle, vasculature, or conductive system. More than 50 ICCs have now been recognised as our diagnostic capabilities improve. However, whilst our understanding of ICCs and their molecular basis has increased, diagnosis and management of these conditions remains challenging owing to their heterogeneity, both genetically and phenotypically.

Sudden death may be the first presentation of ICC, and a new diagnosis has significant implications for patients and family members. Risk may be augmented by a multitude of clinical and genetic factors, which we do not fully understand. There is an urgent need for tools for clinicians to identify patients with ICCs, and identify those with ICCs at increased risk of adverse outcome. Biomarkers, including blood, imaging, genetic and clinical biomarkers may be help diagnosis patients with ICCs, improve prognostication/risk stratification and monitor treatment and disease progression

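### Section 5.2 relies on tests that need quantitative markers to be grouped, fixes no cut-off or grouping rule, and does not say how markers enter the regression and Cox models

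*Combined protocol and SAP*

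**What the plan says.** Section 5.2 is the only description of the analysis. It names four sets of methods:

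- Models: "Multivariable regression modelling will be used to examine relationships between cardiac biomarkers and cardiovascular disease while adjusting for baseline differences of subjects".
- Categorical clinical variables: "Chi square or Fisher exact tests will be used to compare categorical variables between patients with different marker levels".
- Continuous clinical variables: "Independent samples t tests or Mann Whitney U tests will be used to compare continuous variables between patients with differing marker levels".
- Outcome: "Survival analysis will use logrank testing and Cox regression".

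In the second and third of these, the clinical variable is what is compared and the marker defines the groups. Nothing in the document says how those groups are formed: there is no cut-off value, quantile, reference limit or rule for choosing one. Nor does it say whether the marker is continuous or grouped in the multivariable and Cox models.

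The markers are of several kinds. Section 2 refers to "Biomarkers, including blood, imaging, genetic and clinical biomarkers". Section 1.1 says that blood will be "stored to allow measurement of blood biomarkers relating to the heart, including genetic analysis, which will be related to the clinical parameters and outcome". On study size, section 1.1 says: "The expectation is to recruit 1000 patients".

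**The concern.** A blood concentration is a quantitative measurement. To use it in a t test or Mann Whitney test as section 5.2 words them, someone must choose a value that separates one group from the other. This raises two problems.

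First, a split treats all patients on one side as alike, and patients just above and just below the cut as different. If the true relation is graded, this weakens the comparison.

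Second, the choice of cut is open. Clinical data are recorded at the clinic visit (section 4.6.1), follow-up runs for 10 years (section 4.6.2), and blood is stored for later measurement. Nothing requires the cut to be fixed before marker results are linked to those data. A cut chosen because it gives the clearest separation carries a false-positive rate above the nominal one and tends not to replicate.

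The sole objective in section 3 is the diagnostic and prognostic utility of biomarkers, so both effects bear on the study's answer.

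**Working it through.** **The plan's own figure.** Section 5.1 expects about 200 participants a year for 5 years: 200 × 5 = 1000, which agrees with section 1.1. This is an accrual count. The plan gives no power, significance level, effect size or event rate, so the figures below rest on assumptions stated here: two-sided 5% tests, n = 1000 and, for step 1, a normally distributed marker (possibly after a log transformation) with a linear relation to the clinical variable.

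**1. Information kept by a two-group split.** With a proportion p of patients below the cut, z_p the matching normal quantile and φ the normal density, the share of information kept is φ(z_p)² / [p(1 − p)].

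| Cut | φ(z_p) | p(1 − p) | Share kept | 1000 patients act like |
|---|---|---|---|---|
| Median | 0.3989 | 0.2500 | 0.637 | 637 |
| Top quartile | 0.3178 | 0.1875 | 0.539 | 539 |
| Top decile | 0.1755 | 0.0900 | 0.342 | 342 |

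The median is the best case, so under these assumptions the loss is at least 1 − 0.637 = 36%.

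**2. What this does to power (Fisher z approximation).** A continuous analysis of 1000 patients has 80% power at a correlation of tanh[(1.960 + 0.842)/√997] = 0.0885. A median split reduces the correlation to 0.0885 × √0.637 = 0.0706, and power falls to 61%. It is 54% with a top-quartile cut and 37% with a top-decile cut.

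**3. What this does to a logrank comparison.** Assume, for illustration, a hazard ratio of 1.3 per standard deviation of the marker and 80% power. The continuous analysis needs (1.960 + 0.842)² / (ln 1.3)² = 115 events after rounding up. A two-group comparison needs roughly 115/0.637 = 181 at a median split and 115/0.539 = 214 at a top-quartile cut, again rounded up.

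**4. How far the loss depends on the assumptions.**
- Ordered groups scored by their means keep 79.3% with tertiles and 86.1% with quartiles, so they lose 20.7% and 13.9%.
- For a uniformly distributed marker, a median split keeps (1/16)/(1/12) = 75%, a loss of 25%.
- If the true relation is a step located at the cut, a split there loses nothing.
- A marker that is already categorical, such as a genotype, loses nothing.

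**5. False-positive rate if the best-looking cut were chosen.** Simulated with no association, n = 1000, 10,000 or more data sets per scenario, taking the smallest t-test p value over the candidate cuts:

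| Candidate cuts | False-positive rate |
|---|---|
| One cut fixed in advance | about 5% |
| Best of three quartiles | about 12% |
| Best of nine deciles | about 24% |
| Best of all cuts from the 25th to the 75th percentile | about 31% |
| Best of all cuts from the 10th to the 90th percentile | about 46% |

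Repeat runs agree to within about one percentage point.

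**The case against.** The strongest reply is that section 5.2 opens with multivariable regression and closes with Cox regression. Both can take a continuous marker, and neither is said to use a grouped one. The group tests can fairly be read as descriptive companions to those models. The section speaks only of "patients with differing marker levels": it never mentions two groups, a median or a high-versus-low split, and the chi square, Fisher and logrank tests all allow three or more groups. The size of any loss depends on a marker distribution and a shape of relation that the plan does not give. Some markers are categorical by nature. No cut-off search is planned, so the rates above 5% describe a misuse and not the stated method.

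Most of this stands, and it sets the limits of the point. A reader might infer that section 5.2 dichotomises markers throughout and so discards a third or more of the study's information. The documents do not support that: the two-way split is implied only by the t and Mann Whitney tests, and the loss is shown only for the group comparisons and the logrank test.

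The reply does not remove the gap. The plan does not rank the group tests below the models, does not say how the marker enters the models, and does not say how groups are formed. For relating a quantitative marker to a continuous clinical variable, a two-group test is a weaker method than available alternatives that need no extra data.

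**Conclusion.** The point holds in a limited form. The t and Mann Whitney comparisons imply a two-group split of quantitative markers, and the chi square, Fisher and logrank tests imply marker groups of unstated number. No cut-off or grouping rule is fixed in advance, and the marker's form in the multivariable and Cox models is unspecified.

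For a roughly normal marker with a linear relation, a two-group split loses at least 36% of the information in the affected comparisons, and more at an off-centre cut. This does not extend to three or more ordered groups, to genetic or other categorical markers, or to models that keep the marker continuous.

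A reader might also take 12% to 46% as the false-positive rate of this plan. It is not. Those rates apply only if a cut is picked for its result, which the plan neither proposes nor prevents; one cut fixed in advance holds about 5%.

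This is a low-cost improvement that should be made. It does not make the planned tests invalid.

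**What to change.** In section 5.2:

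- State that each quantitative marker enters the multivariable and Cox models as a continuous variable in the primary analysis, transformed if skewed and with non-linearity allowed, for example by a spline. Other ways of allowing for non-linearity are also defensible; what matters is to fix one in advance.
- For continuous clinical variables, use rank correlation or regression on the marker in place of the two-group tests. For categorical ones, use logistic regression.
- Keep grouped tests and logrank curves as descriptive displays, with the number of groups and the cut-offs fixed before marker data are linked to clinical data, for example cohort tertiles or an assay reference limit.
- Label any cut-off derived from the data as exploratory.
- Leave genetic and other categorical markers in their natural groups.

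The change takes a few sentences and needs no new patients, samples or data. The downside is that results are slightly less simple to present than high-versus-low groups.
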